14.5.3. Physical Examination

For each item of physical examination, the frequency and proportion of normal/abnormal subjects will be provided.

15. Safety Assessment Criteria and Methods, and Reporting Methods

15.1. Method of Safety Assessment

Confidential Page 36 of 51

Items for safety assessment include adverse events, vital signs, laboratory tests, and physical examinations. The investigator will examine the subjects at each visit and record all safety assessments performed according to the scheduled procedures.

The results of the laboratory tests are classified into normal and abnormal (NCS, CS) according to the normal range. If the laboratory test result after the administration of the investigational product is judged to be clinically significant compared to before administration, conditions for the abnormal value should be recorded, and it should be assessed as an adverse event.

In addition, if comparison between before and after the administration of the investigational product is assessed as a clinically significant change during the safety assessment such as vital signs, physical examinations, etc., it should be recorded in the adverse event section of the case record.

15.2. Adverse Events

15.2.1. Definition of Adverse Events

1) Adverse Event (AE)

All harmful and unintended sign(s) (includes abnormal results, etc. of the laboratory tests), symptom(s), or disease(s) that occur to subjects receiving the investigational product which need not be causally related to the investigational product.

2) Adverse Drug Reaction (ADR)

All harmful and unintended reactions occurring at any dose of the investigational product, which cannot deny the causal relationship with the investigational product.

3) Unexpected Adverse Drug Reaction

Differences in the pattern or severity of abnormal drug reactions in light of available drug information, such as the investigator's brochure or support documents of the drug.

4) Serious Adverse Events/Adverse Drug Reaction

Any of the following adverse events or adverse drug reactions occurring at any dose of the investigational product

- In case of death or life-threatening cases
- In case where hospitalization is necessary or hospital stay needs to be extended
- In case of permanent or significant failure or degradation of function
- In case of malformations or abnormalities in the fetus

In addition to the circumstances listed above, if a situation occurs that would have a clinically significant impact on the health and well-being of the subjects, it should be determined whether or not the subject will be considered a serious adverse reaction, based on the medical judgment of the investigator and related professionals and proper measures should be taken.

However, in the case of the following subjects, it is not regarded as SAEs.

- ① Subject chooses hospitalization prior to the clinical study or hospitalization for planned treatment/surgical procedure and extension of the hospitalization period for the existing concurrent illness not worsened during the study period (admission to a rehabilitation institution from before taking the investigational product, admission to a nursing home, or a nursing home to inspect admission and laboratory performance abnormalities, if the subject is living far away from the hospital, or doesn't have a caregiver at home, etc.)
- ② Discharge within 24 hours after hospitalization (visit to the emergency room not causing hospitalization)

Confidential Page 37 of 51

5) Special cases (pregnancy): Exposure to the investigational product during pregnancy

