15.2.4. Reporting Methods of Serious Adverse Events

The principal- and sub-investigators should notify Daewoong Pharmaceutical Co., Ltd. of all SAEs occurring during the treatment period of the investigational product within 24 hours after coming to know about them or by the following working day at the latest (based on business days) regardless of the causal relationship with the investigational product by phone or fax ([contact], [contact]) or report to the contract research organization (relevant monitoring staff). And, the report should also be made to the IRB according to the safety reporting procedures of each study site.

Where possible, the initial report should include all items on the SAE Form and all completed forms should be sent to the sponsor. The investigator should complete the adverse event page of the case record form, in addition to the SAE Form. If necessary, a follow-up report containing all new information on SAEs should be completed on the SAE Form and sent to the sponsor.

After receiving the initial report, the sponsor and the IRB should review the information and, if

Confidential Page 39 of 51

necessary, contact the investigator for further information. After reviewing the information on adverse events, the causal relationship with the investigational product should be investigated.

The sponsor will report to the Minister of Ministry of Food and Drug Safety within the following time period if serious or unexpected adverse drug reaction occurs:

- If it causes death or life-threatening: Within 7 days from the date on which the sponsor
 was notified of or learned the relevant fact. In this case, detailed information on adverse
 drug reactions should also be reported within 8 days of the initial reporting date.
- For all other serious and unexpected adverse drug reactions: It should be reported within 15 days from the date on which the sponsor was notified of or learned about the relevant fact.

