6.5.4 Serious Adverse Event

Serious Adverse Event (SAE) means one of the following adverse events or adverse drug reactions that occur at any dose of an investigational product.

- In case of death or life-threatening
- In case where hospitalization is necessary or hospital stay needs to be extended
- In case of permanent or significant failure or degradation of function
- In case of malformations or abnormalities in the fetus

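### Protocol 15.2.1 does not confine its 24-hour-discharge exclusion to the hospitalization criterion, so a life-threatening or medically significant event with a short stay can be read as not an SAE

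*Protocol*

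**What the plan says.** Protocol 15.2.1, item 4, has three layers.

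- **Criteria.** An event is serious if it meets any of four. The first is "In case of death or life-threatening cases" and the second is "In case where hospitalization is necessary or hospital stay needs to be extended". The other two concern lasting loss of function and fetal abnormality.
- **Judgment clause.** Beyond the list, "if a situation occurs that would have a clinically significant impact on the health and well-being of the subjects", the investigator and other professionals decide on medical grounds whether it counts as serious.
- **Exclusions.** These come last: "However, in the case of the following subjects, it is not regarded as SAEs". The first covers planned, elective or social admissions for conditions that have not worsened. The second is "Discharge within 24 hours after hospitalization (visit to the emergency room not causing hospitalization".

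Protocol 15.2.4 obliges investigators to notify the sponsor "of all SAEs occurring during the treatment period of the investigational product within 24 hours after coming to know about them", or by the next working day. The sponsor's report to the ministry then has its own clock: "If it causes death or life-threatening: Within 7 days from the date" on which the sponsor was told or learned of the event, and 15 days for other serious and unexpected reactions.

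SAP 6.5.4 opens with "Serious Adverse Event (SAE) means one of the following adverse events or adverse drug reactions that occur at any dose of an investigational product" and lists the same four criteria. It has neither the judgment clause nor the exclusions.

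**The concern.** The exclusion follows both the criteria and the judgment clause, opens with a word of contrast, and removes SAE status as such. It does not say that a short stay fails the hospitalization criterion, and it has no saving words for an event that is serious on other grounds. A site that applies the text as written could therefore classify as non-serious an event that the same item calls serious.

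What is at stake is mainly the speed and route of reporting. Investigator notification in 15.2.4 depends on SAE status, and the sponsor's 7-day and 15-day clocks start only once the sponsor knows. Protocol 14.5.1 also compares SAE incidence between arms and asks for a detailed report on each SAE. An event set aside at the definition would miss that handling.

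**Working it through.** No arithmetic applies, because the point concerns the wording of a definition. The check takes types of event through three readings: the second exclusion as literally written, the same exclusion limited to the hospitalization criterion, and SAP 6.5.4.

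| Event | 15.2.1, exclusion read literally | 15.2.1, exclusion limited to hospitalization | SAP 6.5.4 |
|---|---|---|---|
| A. Life-threatening, emergency room only | Not an SAE | SAE (first criterion) | SAE (first criterion) |
| B. Life-threatening, admitted, discharged within 24 hours | Not an SAE | SAE (first criterion) | SAE (first criterion) |
| C. Judged medically significant, emergency room only | Not an SAE | SAE (judgment clause) | Not an SAE (no such clause) |
| D. Judged medically significant, admitted, discharged within 24 hours | Not an SAE | SAE (judgment clause) | SAE (through hospitalization) |
| E. Serious through hospitalization only, discharged within 24 hours | Not an SAE | Not an SAE | SAE (through hospitalization) |
| F. Judged medically significant, no hospital contact | SAE (judgment clause) | SAE (judgment clause) | Not an SAE (no such clause) |

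Four things follow.

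1. In rows A to D the literal reading contradicts the protocol's own first criterion or judgment clause. These are the rows that matter.
2. Row E is excluded on both protocol readings. A short stay that is serious only because of the admission is not part of the problem, and the clarification would not make it an SAE.
3. Rows A and C depend on how the parenthesis about emergency-room visits is taken. It may merely explain the phrase before it, or it may be a second excluded case. A visit without admission would not ordinarily meet the hospitalization criterion. If the parenthesis has any effect of its own, that effect falls on events serious by another route.
4. The SAP differs in both directions. It is broader where it drops the exclusions (row E, and A, B and D against the literal reading) and narrower where it drops the judgment clause (rows C and F). The SAP's table of changes from the protocol (section 14), as far as it can be read, lists only the determination of gallstones.

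For rows A to D under the literal reading, the investigator's duty in 15.2.4 does not apply. The event still goes on the case record form under 15.2.3 with severity, causality, seriousness and action taken, and SAP 9.2.2 tabulates it as a TEAE.

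**The case against.** The strongest reply is that the exclusions were meant only to say what does not count as hospitalization. Both describe hospital stays, the threat-to-life criterion stands separately in a list where any one item suffices, and nothing in the text says that a life-threatening event loses SAE status. The document is also a translation, so fine points of phrasing carry limited weight. This stands as an account of probable intent. It does not remove the defect, because sites work from the written text, which states no such limit.

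A reader might infer four stronger things that the documents do not support.

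- **The protocol deliberately removes life-threatening events from SAE status.** That follows only from unqualified wording. Fatal events are not realistically affected, since they do not end in discharge.
- **Safety signals would be lost.** AE recording and tabulation are untouched. Protocol 18.3 also requires events that may affect patient safety to go to the IRB, which is wider than SAEs alone. The exposed part is rapid notification of the sponsor and what depends on it.
- **The SAEs reported and the SAEs tabulated will differ.** The SAP wording does differ, but SAP 9.2.3 only tabulates serious events, and no section provides for reclassifying them against 6.5.4. If the tables use the investigator's seriousness entry on the case record form, the counts follow the protocol definition.
- **The effect can be sized from the protocol's gallstone figures.** Multiplying the assumed stone rates (18% and 7% in section 8.3) by the 10-20% symptomatic share in section 5.2 counts symptomatic stones. What matters is short-stay events that also meet another criterion. Many biliary attacks with a brief stay would be serious only through hospitalization (row E). The 10-20% is not a 12-month figure, and subjects with ultrasound-confirmed stones leave the study under 13.2.

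**Conclusion.** The point holds as a defect of scope. As written, the second exclusion in 15.2.1 contradicts the threat-to-life criterion and the judgment clause for events treated in the emergency room or discharged within 24 hours, and on that reading it switches off investigator notification under 15.2.4. The SAP definition differs in wording and should be reconciled, but a difference in counts is not shown.

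The size cannot be given. The affected events are those with a stay under 24 hours, or an emergency-room visit, that also meet another seriousness criterion, and the documents offer no basis for their number. The practical effect further assumes that a site follows the literal text. Efficacy analysis, sample size and AE collection are not affected. The case for acting rests on subject protection: the contradiction sits in the definition that triggers expedited reporting.

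**What to change.** Replace the second exclusion in Protocol 15.2.1, item 4, with a sentence to this effect: an emergency-room visit or a hospital stay of less than 24 hours does not by itself meet the hospitalization criterion; the event remains an SAE if it meets any other seriousness criterion, including the medical-judgment clause.

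Use the same definition in SAP 6.5.4, with both the judgment clause and the clarified exclusions, and state there whether the serious-event tables are built from the seriousness field on the case record form.

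The cost is one protocol sentence, a matching SAP definition, and a few more SAE forms for short but otherwise serious events. Design, sample size and treatment are unchanged.

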15.2.2. Assessment Criteria

The investigator will assess adverse events according to the following criteria for severity and causal relationship.

Assessment of severity

The severity of an adverse event is indicative of the severity of the condition and should be assessed separately from the severity of life-threatening, functional decline, or condition requiring treatment. The severity is evaluated according to the following criteria:

- Mild: Showing symptoms or signs but without hindrance to daily life
- Moderate: The degree to which routine activities are restricted and sufficiently inconvenienced
- Severe: To the extent that daily activities cannot be carried out

2) Assessment of the causal relationship with investigational product

The investigator evaluates the causal relationship between the investigational product and the adverse event on the basis of the following criteria. And all adverse events are considered adverse drug reactions unless evaluated as "probably not related" or "definitely not related."

Definitely related

- If there is evidence that the investigational product has been administered and the time sequence of adverse events is reasonable
- If the adverse event is most likely explained by the administration of the investigational product more than any other reasons
- If adverse events disappear as a result of discontinuation of administration
- If re-administration (only if possible) result is positive
- If the adverse event is consistent with information already known about the investigational product or the same type of drug

② Probably related

- If there is evidence that the investigational product has been administered and the time sequence of adverse events is reasonable
- If the adverse event is most likely explained by the administration of the investigational product more than any other reasons
- If adverse events disappear as a result of discontinuation of administration (only if performed)

③ Possibly related

- If there is evidence that the investigational product has been administered and the time sequence of adverse events is reasonable
- If the adverse event is believed to be due to the administration of the investigational product at the same level as other potential causes
- If adverse events disappear as a result of discontinuation of administration (only if performed)

Probably not related, Unlikely

- If there is evidence of administering the investigational product
- If there are other more likely causes for the adverse event
- If suspension of administration (if performed) result is negative or unknown

Confidential Page 38 of 51

- If re-administration (if performed) result is negative or unknown
- (5) Definitely not related; None
- If the subject has not received the investigational product
- If the time sequence between the administration of the investigational product and the development of the adverse event is not feasible
- If there is another obvious cause for an adverse event
- 6 Unknown, Unassessable
- If information cannot be judged because it is insufficient or conflicting and cannot be supplemented or verified.

15.2.3. Reporting of Adverse Events

Adverse events are those in which unexplained symptoms that appeared before the administration of the investigational product, either during the period of administration, or before the administration of the investigational product, and increased during the treatment period, regardless of the causality with the investigational product (including abnormal levels in clinical pathology), symptoms or illnesses, etc.

Adverse events should be monitored until the time of recovery to the status before treatment with the investigational product or the reference value, or until the investigator can determine that the adverse event has become normal or until further observation is deemed unnecessary. However, any new signs or symptoms that occur 30 days after the last administration of the investigational product will not be considered as adverse events.

Information on adverse events detected by the investigator during scheduled or unscheduled visits during the period of collection of adverse events should be recorded in the case record form, and the information to be collected is as follows:

- Name of adverse events (including the start date/date of disappearance, etc.)
- Assessment of severity (See Section 1 of 15.2.2)
- Causal relationship with the investigational product (See Section 2) of 15.2.2)
- Seriousness
- · Actions taken for investigational product
- · Measures made to treat the adverse event

15.2.4. Reporting Methods of Serious Adverse Events

The principal- and sub-investigators should notify Daewoong Pharmaceutical Co., Ltd. of all SAEs occurring during the treatment period of the investigational product within 24 hours after coming to know about them or by the following working day at the latest (based on business days) regardless of the causal relationship with the investigational product by phone or fax ([contact], [contact]) or report to the contract research organization (relevant monitoring staff). And, the report should also be made to the IRB according to the safety reporting procedures of each study site.

Where possible, the initial report should include all items on the SAE Form and all completed forms should be sent to the sponsor. The investigator should complete the adverse event page of the case record form, in addition to the SAE Form. If necessary, a follow-up report containing all new information on SAEs should be completed on the SAE Form and sent to the sponsor.

After receiving the initial report, the sponsor and the IRB should review the information and, if

Confidential Page 39 of 51

necessary, contact the investigator for further information. After reviewing the information on adverse events, the causal relationship with the investigational product should be investigated.

The sponsor will report to the Minister of Ministry of Food and Drug Safety within the following time period if serious or unexpected adverse drug reaction occurs:

- If it causes death or life-threatening: Within 7 days from the date on which the sponsor
 was notified of or learned the relevant fact. In this case, detailed information on adverse
 drug reactions should also be reported within 8 days of the initial reporting date.
- For all other serious and unexpected adverse drug reactions: It should be reported within 15 days from the date on which the sponsor was notified of or learned about the relevant fact.

The investigator is responsible for reporting special cases (if pregnant) even if they do not correspond to a SAE. The investigator instructs female subjects to notify him/her immediately if she becomes pregnant during the study period If female subjects become pregnant after taking the investigational product, the investigator will promptly report all pregnancies (within 24 hours of occurrence) according to the SAE reporting method, even if no adverse events occur. In addition, pregnancy is not considered to be a SAE/ADR, but they should be dropped out from the study. And, the progress of pregnant women and fetuses should be tracked and reported until 30 days after delivery.

16. Informed Consent form, Compensation Rules, and Diagnosis and Treatment of Subjects after Study

16.1. Informed Consent Form for Subjects

The principal-/sub-investigators will fully explain to the subject the purpose and method of the study, the effect and adverse events of the investigational product in advance and obtain an informed consent from the subject.

Appendix 4. See the Informed Consent Form for Subjects

16.2. Compensation Rules for Victims

Appendix 5. See the Compensation Rules for Victims

16.3. Diagnosis and Treatment of Subjects

Subjects who are dropped out of the study or who show no therapeutic effect should be given other proper treatment. Subjects who have completed the study should select the best treatment method according to the investigator's judgment.

17. Measures to Protect the Safety of Subjects

This study will be conducted scientifically and ethically in accordance with the KGCP and the relevant laws and regulations related to clinical studies. In addition, this study will be conducted in accordance with the Declaration of Helsinki in order to respect human dignity and rights, and to prevent disadvantages to the subjects.

The study site conducting the study should be equipped with facilities and the professional staff necessary for carrying out the study and should be ready to carry out the study appropriately.

The IRB will evaluate and approve the protocol in accordance with the GCP and will periodically evaluate whether the study is proceeding according to the protocol.

Confidential Page 40 of 51

The investigators should thoroughly confirm that the subjects are healthy enough to participate in the study by checking the health status of each subject before they are enrolled in the study. In addition, the investigator should be fully familiar with the protocol and the investigational product, and carry out the study according to the protocol. He/she will do their best to ensure the safety of the subjects, and if adverse events occur due to the study, appropriate medical actions should be taken until the patient recovers.

If the subject wishes to be treated due to an adverse event during the study period or if the investigator considers that medical treatment is necessary, he/she should immediately visit the study site conducting the study and receive relevant tests such as blood pressure measurement, laboratory tests, etc. If the investigator judges that the study should be stopped by evaluating the adverse events and the test results, or if the subject wants to discontinue the study, the investigator should promptly proceed with the procedure according to the termination of the study and actively carry out the treatment that can alleviate the corresponding symptoms of the subject.

18. Other Requirements for Safe and Scientific Implementation of Study 18.1. Good Clinical Practice (GCP, ICH E6)

The procedures set out in this protocol are designed to ensure that the sponsor and the investigator comply with the essential spirit of the Good Clinical Practices (KGCP, ICH E6) and the Declaration of Helsinki in conducting and evaluating this study and documenting the results.

